### 6.3 Location of study.

This study will be conducted at the HBOC clinics at St. Luke's Health System in Kansas City, Missouri and Medstar Washington Hospital Center in Washington, DC.

### 6.4 Description of recruitment strategies.

Participants will be identified through the scheduling system at St. Luke's Health system HBOC clinic. The scheduling coordinator will identify participants on the schedule who may meet criteria for the study. During the routine reminder call to patients the coordinator will ask clients if they are willing to receive a phone call regarding a study. If clients agree the AI will contact clients to explain the study, identify clients interest, and complete the informed consent. Clients will also be sent an information leaflet (See appendix G) about the study in the pre-appointment packet that is sent to all clients to provide informed about the study before the AI contacts them.

Recruitment will occur in a similar fashion at Medstar Washington Hospital Center although the clinic does not have a single clinic coordinator. For this reason, the counselor will oversee the identification of participants who may qualify for the study. To minimize conflict of interest, clinic personnel other than the genetic counselors will then call the potential patient participants to seek permission for them to be contacted by the AI. If they agree, the AI will contact them in the same manner as at St. Luke's Health system.

Genetic counselor participants at St. Luke's Health System were contacted for interest in hosting the study through the National Society of Genetic Counselors cancer Special Interest Group (SIG). The two counselors at St. Luke's Health system voluntarily contacted the AI to both assist with this research at their site and to participate. The counselors at Medstar Washington Hospital Center were contacted by the AI after initial IRB approval in order to increase recruitment by adding an additional site.

### 6.5 Description of criteria for withdrawal from study.

Client participants may withdraw from the study at any time during or immediately following completion. While completing the survey, the participant may choose not to answer any particular question. Surveys will be anonymous, using a code word to coordinate documents (see Section 10) and never linked to contact information. If client participants request to withdraw from the study if they must provide their code word to identify and remove their documents.

Genetic counselor participants may with withdraw from the study at any time during the study. If genetic counselor participants withdraw any previous surveys will be included in the analysis but future patients will not be consented to participate. Surveys will not be linked to the individual counselor.

## **7.0 Description of study statistical considerations and/or analytic plan:**

*Aims have been copied here for ease of interpretation.*

Aim 1: To assess the preliminary impact of a novel SA intervention on outcomes that may be targeted in future studies, by assessing differences in the following between a SA intervention and unaffirmed standard SA intervention control group of HBOC genetic counseling clients:

- a. Intentions to talk with family, test uptake
- b. Empowerment, decision self-efficacy
- c. HBOC knowledge

The primary goal of analysis of aim 1 is to identify which outcomes would be most appropriate for follow up studies and the necessary sample size for adequate statistical power.

For decision efficacy, the scores on the Decision Self-Efficacy Scale (See section 2 of client survey, Appendix D) will be compared between groups using linear regression controlling for education, race, anxiety score, and effectiveness of intervention (based on last question on intervention Appendix C). Intention to talk with family, genetic testing uptake, and information seeking will be measured similarly using linear regression.

Client empowerment will be analyzed by using the GCOS-24 a 24-item likert scale completed by clients and parallel scale by genetic counselors (See section 3 of client survey of appendix D and appendix F). Both scales will be compared between groups using linear regression controlling for education, race, anxiety score, and effectiveness of intervention (based on last question on survey). Discrepancies between counselor and client surveys will be analyzed using dyadic analyses. For this analysis, we will assess the correlation between paired client and genetic counselor GCOS-24 for the compete survey and for the individual questions.

HBOC knowledge will be analyzed between groups using linear regression testing the knowledge scale (See section 4 of client survey, Appendix D) and controlling for education, race, anxiety score, and effectiveness of intervention.

Effect sizes and standard deviations for each outcome will be identified, and an estimated sample size for a fully powered study will be estimated based on power calculations.

Aim 2: To describe genetic counselors' (GCs) and clients' response to a novel, client-based SA intervention, including perceived impact, barriers, and facilitators to implementing such an intervention on a wider scale

This aim will be analyzed as percent of yes/no response to intervention survey questions for both clients and counselors. There will also be open ended questions for specific impacts, barriers, and facilitators to be mentioned, which will be analyzed using thematic analysis of answers. The AI will create a codebook based on initial read through and subsequently code all answers. A separate coder will validate ten percent of answers for consistency.

Aim 3: To assess the percentage of clients that completed a pre-visit SA intervention among client participants and if the SA intervention is affective in affirming clients.

Intervention uptake will be reported as a percentage of participants who were eligible based on counselor referral and who were contacted by AI that completed the SA intervention and client survey. Effectiveness of affirmation is an internal control and will be assessed by screening the last question on the intervention for those in the intervention group who report higher than a 2 and those in the control group who report lower than a 5. Additionally, transcripts of intervention essays will be analyzed for affirmation themes.

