SA is postulated to decrease patient defensiveness. To our knowledge there are no direct measures of patient defensiveness but this construct has been assessed by measuring numerous downstream constructs in past research, including perceived threat, message acceptance, and defensive avoidance (Good & Abraham, 2007). In this study, we will be measuring the downstream effects of defensiveness by assessing patient empowerment and decision efficacy. SA interventions are theorized to decrease patient defensiveness, which will increase their openness to threatening information, which will increase decision self-efficacy. Furthermore, increased openness will increase the client's engagement in the genetic counseling session and result in greater patient empowerment. It is also possible that client self-integrity, their global sense of personal adequacy, is related to empowerment more directly than outlined above.

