### **Intervention (See appendix C)**

For the SA intervention, participants will be asked to rank 11 items (artistic skills, athletics, business/money, creativity, independence, music, politics, relationships with friends and family, religious values, sense of humor, spontaneity) from most important to least important (Creswell et al., 2013; Havranek et al., 2012). They will then be asked to write about the item that is most important to them and why it may be important to them. The control group will rank the same list and be asked to will write about the 9th ranked item and why it might be important to someone else. The control condition is consistent with the control used in other SA intervention studies.

Immediately after the intervention or control condition, participants will complete a 2 minute survey that consists of the short version of the Stat-Trait Anxiety Inventory (STAI). This measurement entails 6 questions to assess the client's current anxiety. The purpose of the STAI is to control for anxiety, to identify if those who are more anxious are more effected by the SA intervention. The intervention and STAI should take about 10-15 minutes together. At the end of the intervention there will be a detachable page asking for the client's email address to send them with the post-intervention survey and a reminder to complete it. This document will be immediately separated from the study material by the scheduling coordinator.

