## **9.0 Description of likelihood and seriousness of harms and how safety will be maximized:**

This study is unlikely to cause serious harms. There is small chance that there could be low level psychological harm caused by this study because SA has been shown to increase openness to a threatening message and therefore increase feelings of vulnerability and possibly anxiety (Klein et al., 2011). While this may occur among participants in the intervention arm, the magnitude of the risk is likely small and will be mitigated by the fact that they will be seen by genetic counselors who have training to manage clients' anxiety. There also could be benefit to increasing anxiety in a situation where action needs to be taken to avoid a threat, such as continuing recommended screening for early detection of breast cancer. There is no increased risk to pregnant women or fetus related to this study protocol.

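### The Aim 1 regressions adjust the arm comparison for two measures taken after the randomised writing task, so the arm coefficient need not estimate the effect of assignment

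*Combined protocol and SAP*

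**What the plan says.** Section 7.0, Aim 1, compares decision self-efficacy between arms by "linear regression controlling for education, race, anxiety score, and effectiveness of intervention (based on last question on intervention Appendix C". Client and counselor GCOS-24 scores are compared with the same four covariates, but the item is sourced differently: "controlling for education, race, anxiety score, and effectiveness of intervention (based on last question on survey". HBOC knowledge has the same list. The remaining outcomes are covered only by reference: "Intention to talk with family, genetic testing uptake, and information seeking will be measured similarly using linear regression". The aim closes with "Effect sizes and standard deviations for each outcome will be identified", to feed a sample size for a full study. It does not name the model these come from.

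Aim 3 in the same section treats the effectiveness item as a check on the affirmation, by screening for "those in the intervention group who report higher than a 2 and those in the control group who report lower than a 5". This is the only coding given for it anywhere.

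On the timing of the anxiety score, section 5.6 says: "Immediately after the intervention or control condition, participants will complete a 2 minute survey". Section 5.0 says only that it comes before the appointment and accompanies the writing prompt, which does not conflict.

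**The concern.** A covariate may safely enter a randomised comparison if the randomised treatment cannot have changed it. Neither of these two qualifies.

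The effectiveness item is meant to differ by arm, and affirmation is the mechanism by which the protocol expects outcomes to move. Section 3.0 sets out the chain: "SA interventions are theorized to decrease patient defensiveness, which will increase their openness to threatening information, which will increase decision self-efficacy". Holding a score for affirmation constant asks how the arms differ among clients who are equally affirmed. Aim 1 needs the difference produced by assignment. Unmeasured causes shared by the item and the outcome can add further bias.

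The anxiety score follows the exercise, and section 9.0 says self-affirmation may "increase feelings of vulnerability and possibly anxiety". It therefore mixes prior anxiety with any effect of the task.

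These regressions are the only arm comparisons specified, and the stated primary goal of Aim 1 is to pick outcomes and a sample size for follow-up. If the planning effect sizes come from them, an outcome that responds to self-affirmation could look unresponsive and be dropped, and the next sample size would be unreliable.

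**Working it through.** **Inputs from the documents.** 35 clients per arm (section 5.0). For a full study, d = 0.35, alpha 0.05, a value of 0.85 labelled beta, and N = 296 (section 6.1). The documents do not give the item's scale, direction or reliability, its arm difference, its relation to outcomes, or any shift in anxiety. Values for these below are assumptions.

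**The plan's own figure.** Total N = 4(z₀.₉₇₅ + z₀.₈₅)²/d² = 4 × (1.960 + 1.036)²/d² = 35.9136/d² with unrounded quantiles. At d = 0.35 this is 35.9136/0.1225 = 293. The two-sided t-test version gives 148 per arm, 296 in total, an exact match. One-sided testing gives 236 and 80% power gives 258. So 0.85 is power and the test is two-sided. The 296 rests on an outside effect size and is not affected by this point. N = 35.9136/d² is used below.

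**Bias formula.** In a two-arm linear model with one added covariate M:

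adjusted arm coefficient = total effect − λδ,

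where λ is the within-arm slope of the outcome on M and δ is the arm difference in M.

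**Check entered as a raw score.** Let a share p of the effect pass through affirmation, measured by the item with reliability r. Then λδ = p·r·d, and the adjusted coefficient is d(1 − p·r). The size of the manipulation and the direction of scoring both cancel.

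| r | p | Adjusted coefficient | Next-trial N |
|---|---|---|---|
| 0.8 | 0 | 0.35 | 293 |
| 0.8 | 0.25 | 0.35 × 0.80 = 0.28 | 458 |
| 0.8 | 0.5 | 0.35 × 0.60 = 0.21 | 814 |
| 0.8 | 1 | 0.35 × 0.20 = 0.07 | 7,329 |
| 0.5 | 0.5 | 0.35 × 0.75 = 0.2625 | 521 |
| 0.5 | 1 | 0.35 × 0.50 = 0.175 | 1,173 |

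Simulations with 35 per arm agree with this closed form.

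Shared causes can make λ differ from the value mediation implies. Setting λ directly, with M in within-arm SDs:

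- δ = 1 and λ = 0.1, 0.2, 0.3: 0.25, 0.15, 0.05.
- δ = 1.5 and λ = 0.3: 0.35 − 0.45 = −0.10, past zero.
- δ = 1 and λ = −0.1: 0.35 + 0.10 = 0.45, an upward bias.
- λ = 0: no bias.

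**Precision.** Correlation between arm and item inflates the variance by 1 + δ²/4, which is 1.25, 1.56 and 2.0 at δ = 1, 1.5 and 2. With λ = 0, the standard error rises from √(2/35) = 0.24 to 0.27, 0.30 and 0.34.

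**Check entered as the Aim 3 flag.** Assuming a 1–7 item, reliability 0.8 and either scoring direction, simulated mean coefficients ran from about 0.31 to 0.41 around the true 0.35. The bias is small and of either sign.

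**Anxiety score.** Assume λ = −0.3. If the exercise raises anxiety by 0.3 SD, the coefficient is 0.35 − (−0.3)(0.3) = 0.44 (N 186). If it lowers anxiety by 0.3 SD, it is 0.35 − (−0.3)(−0.3) = 0.26 (N 531).

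**After the change.** Without the two measures the coefficient averages 0.35 when that is the true effect. The standard error is 0.239 and the 95% interval is ±1.96 × 0.239 = ±0.47.

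**The case against.** The strongest reply is that the direction and size of the bias depend on a coding the plan does not state. The only written definition is the pair of arm-specific cut-offs, and with that flag the bias is small beside a standard error of 0.24. This stands as a limit: bias toward zero is the likely result only if the item enters as a raw score. That is the natural reading of a covariate in these regressions, but Appendix C is not in the available text to confirm it.

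Second, section 9.0 ties possible anxiety to openness to a threatening message, and that message arrives in the session, after the anxiety score is taken. The documents therefore do not establish that the exercise alone shifts the score. This weakens the anxiety point relative to the check. It does not make a post-task score a baseline covariate. Section 5.6's interest in whether anxious clients respond more is a moderation question, which an additive term does not answer.

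Third, effect sizes paired with SDs could be taken from unadjusted means, leaving the planning N untouched. The plan does not say so, so the harm to planning is conditional.

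Fourth, this is a feasibility study in which significance is not expected (section 3.0), and the corrected estimate stays very imprecise. That is true, but the same section wants effect sizes and intervals to size a future trial, so bias in those estimates matters whatever the p-values.

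Finally, the two sources cited for the item may be one. Section 5.0 refers to the writing document as a survey in one place. This needs only clarification, and an item on the post-visit survey would also be post-randomisation.

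**Conclusion.** The concern holds, and the plan should be changed before analysis. Both covariates follow the randomised task, one is designed to differ by arm, and no comparison without them is specified. The covariate list is explicit for decision self-efficacy, both GCOS-24 versions and knowledge. For family communication, test uptake and information seeking it is only implied.

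The size is unknown. For a raw check score the bias is probably toward zero, and under the assumptions shown it ranges from none to nearly the whole effect. For the cut-off flag it is small and unsigned. For the anxiety score it may go either way. The large planning Ns illustrate what could follow if effect sizes are read from these models. They are not predictions.

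**What to change.** In section 7.0:

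- Remove the effectiveness item and the post-exercise anxiety score from the main Aim 1 models for every outcome.
- Compare clients by assigned group among those with outcome data, adjusting only for variables the exercise cannot change: education and race, with site and cancer status optional.
- State that the planning effect sizes and SDs come from this model, and report them with confidence intervals.
- Report by arm how many assigned clients lack a usable outcome, whether from an unreturned survey or an unmatched code word (section 10.3).
- Report the check by arm under Aim 3. Use it and the anxiety score otherwise only in mediation or moderation analyses labelled exploratory.
- Reconcile the two sources cited for the item, and state its scale, direction and coding.

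The cost is rewording, with no new data, so it works for clients already enrolled. Dropping the anxiety score gives up some precision if it is prognostic: at an assumed within-arm correlation of 0.3, 0.3² = 9% of residual variance. Counting missing outcomes by arm is a small extra task and does not itself solve missingness. The change removes a source of bias and leaves the imprecision of 35 per arm as it is.

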#### **5.0 Description of procedures:**

In this intervention-based randomized controlled feasibility study, Hereditary Breast and Ovarian Cancer (HBOC) genetic counseling clients will receive an intervention and short survey before their appointment and will complete a survey after their appointment. Genetic counselors who counsel participating clients will complete a post-appointment survey after each appointment with a participating client and a survey at the end of the study.

Thirty-five client participants will be randomly assigned to complete the self-affirmation intervention and 35 participants will complete the control condition. Client participants will be patients being seen for an initial appointment for genetic counseling at the HBOC genetic counseling clinic, regardless of current cancer status. All client participants will take a state anxiety measure before their appointment to control for some of the variability in indication. Client participants will also indicate if they have cancer, if they have received genetic testing, and if they were offered genetic testing at the current visit. Genetic counseling can be indicated for patients without cancer who have a family history of cancer, for patients with cancer, and for self-referred patients who are concerned about their cancer risk. Most often, the initial cancer genetic counseling appointment occurs before qualification for genetic testing is assessed and clients have a follow-up appointment to receive results. Sometimes oncologists or primary care physicians order genetic tests and the initial genetic counseling appointment includes results delivery and education. Any client with an initial genetic counseling appointment will be invited to participate in the study. Follow-up appointments will not be included because patients already have a relationship with the genetic counselor. The four genetic counselors, who have appointments with the participating clients, will be enrolled in the study as genetic counselor participants.

The SA intervention consists of participants ranking 11 items (artistic skills, athletics, business/money, creativity, independence, music, politics, relationships with friends and family, religious values, sense of humor, spontaneity) from most important to least important (See

[figure not shown]

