9.1 Therapeutic interventions *N/A*

9.2 Diagnostic interventions *N/A*

9.3 Radiation *N/A*

9.4 Sedation *N/A*

9.5 Risks to family relationships and other psychosocial or economic harms *N/A*

## 10.0 Description of how privacy and confidentiality of medical information/biological specimens will be maximized

Code words will be used to coordinate assembly of study documents and identifiable client information will not be connected with study documents. For initial surveys to be matched with post-session surveys for later analysis, clients will choose a code word compiled by asking: What is the first street that you lived on? What was your first pet's name? (e.g. OakMondo). This code word will be put on all documents relating to a given participant. The client will tell the counselor the code word during the appointment in order to label the counselors' post-visit survey, but no record of the code word in association with the client's name will be created. Cancer is a common condition and we do not expect clients to be identifiable through their diagnosis. Code words will be destroyed at completion of the study.

Genetic counselor surveys will not include identifying information for the counselor or which after-visit survey was conducted by each counselor. After-visit genetic counselor surveys will include the client code-word that will aid in confirming that surveys are being completed by counselors.

10.1 Description of any clinical/demographic information that will be included.

For clients, demographic information will be collected including: education, age, sex, race, and clinic site. No demographic information will be collected for counselors.

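### The Aim 1 models adjust for two measures taken after the randomised writing task and leave out cancer status and clinic site, which are already collected and which the task cannot change.

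*Combined protocol and SAP*

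**What the plan says.** Section 7.0 (Aim 1) compares decision self-efficacy between arms by linear regression "controlling for education, race, anxiety score, and effectiveness of intervention". Empowerment (client-rated and counselor-rated) and knowledge get the same four covariates. For the rest, "Intention to talk with family, genetic testing uptake, and information seeking will be measured similarly using linear regression". The effectiveness covariate is the closing item on the writing-task form; the empowerment paragraph places it on the survey instead. Either way it is answered after the task.

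The role of the anxiety score is given in section 5.0: "All client participants will take a state anxiety measure before their appointment to control for some of the variability in indication". Its timing is given under Intervention in section 5.6: "Immediately after the intervention or control condition, participants will complete a 2 minute survey".

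Other information on indication and setting is also gathered. Section 5.0: "Client participants will also indicate if they have cancer, if they have received genetic testing". Later in section 5.0, cancer status is listed on the exit survey. Section 10.1 lists "education, age, sex, race, and clinic site". Neither cancer status, testing history nor site enters any Aim 1 model or sensitivity analysis, and no stratified allocation is described.

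**The concern.** Aim 1 exists to pick outcomes and size a later trial, so what matters is an undistorted estimate of the difference between arms. A covariate helps if it predicts the outcome and the intervention cannot move it. Two of the four planned covariates fail the second condition.

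- **Effectiveness rating.** Aim 3 uses this same item to check whether the task affirmed the intervention group and not the controls. It is meant to differ by arm. Holding it constant asks what the intervention does when it changes nothing in how affirmed clients feel.
- **Anxiety score.** It precedes the session but follows the task. Section 9.0 itself allows that self-affirmation might raise anxiety, although it has the response to the threatening message in mind.

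Meanwhile the plan wants indication controlled but relies on this post-task proxy, when cancer status is a direct marker that is already recorded. Site is also the only recorded variable separating the two pairs of raters behind counselor-rated empowerment, because counselor surveys carry no counselor identifier.

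**Working it through.** **1. The plan's own figure.** Section 6.1 gives 296 for d = 0.35, 0.85 (printed as beta, evidently power) and alpha 0.05. Two-sided normal approximation: n per arm = 2 × (1.960 + 1.036)² / 0.35² = 146.6, so 147 and a total of 294. The t-test version gives 148 per arm, 296 in total. The figure reproduces, so 0.35 is a fair yardstick. With 35 per arm the SE of d is √(2/35) = 0.239.

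**2. What adjusting for a post-task variable can do.** If a share m of the effect passes through the adjusted variable, and nothing else drives both that variable and the outcome, the coefficient for arm becomes d × (1 − m). The required N scales as 1/(1 − m)². The values of m are assumed.

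| m | adjusted d | N implied for the next study |
|---|---|---|
| 0 | 0.35 | 296 |
| 0.25 | 0.35 × 0.75 = 0.26 | 296 / 0.5625 = 526 |
| 0.50 | 0.35 × 0.50 = 0.175 | 296 / 0.25 = 1,184 |

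If something unmeasured drives both the rating and the outcome, the distortion can go in either direction. A covariate correlated r with arm also multiplies the SE by 1/√(1 − r²), before any variance it explains: 1.05 at r = 0.3 and 1.15 at r = 0.5 (both assumed).

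**3. Precision from the baseline factors.** Take N = 70 and k₀ covariate terms already in the model. Adding three terms with extra explained variance R² gives SE ratio = √[(1 − R²)(N − k₀ − 3)/(N − k₀ − 6)]. With k₀ = 4 this is √[(1 − R²) × 63/60].

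| extra R² (assumed) | SE ratio | change |
|---|---|---|
| 0 | 1.025 | +2.5% |
| 0.05 | 0.999 | about 0% |
| 0.10 | 0.972 | about -3% |
| 0.20 | 0.917 | about -8% |

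Break-even is R² = 3/63 = 0.048; for k₀ up to 8 it stays near 0.05. For scale, a 0.5 SD difference by cancer status at 50% prevalence (both assumed) gives R² of roughly 0.5² × 0.25 = 0.06. The table prices additions only. In the swap recommended here two terms leave and two or three enter, so the cost in degrees of freedom is smaller, but any variance the dropped terms explain is lost and is not counted.

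**4. Chance imbalance.** Exact hypergeometric probability, 35 v 35, of an arm difference of at least 20 percentage points:

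- 50% prevalence (assumed): 15%
- 30% prevalence (assumed): 12%
- site, 16 of 70 (the split expected in section 5.0): 4%

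If the number with the factor is not held fixed, the binomial version gives 12% and 9% for the first two. A 20-point imbalance in a factor worth 0.5 to 0.8 SD (assumed) moves the estimate by 0.20 × 0.5 = 0.10 to 0.20 × 0.8 = 0.16 SD. The typical shift is smaller: the SD of the imbalance at 50% prevalence is 0.120, giving 0.06 to 0.10 SD against an SE of 0.239.

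**The case against.** The strongest reply is that this is a feasibility study which does not expect significant results (section 3.0), that indication is already partly addressed by design, and that covariate choice at 35 per arm is largely judgement. State anxiety may predict the outcomes well; if the short task barely shifts it, adjusting for it would help, and dropping it could cost precision. That stands as a real downside, because the documents give nothing to settle it. It does not rescue the effectiveness rating, which the task is designed to change.

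Three stronger readings are tempting and are not supported:

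- **A reader might infer that omitting site and cancer status biases the comparison.** It does not on average. Under randomisation, chance imbalance is random error, already reflected in the confidence interval.
- **A reader might infer that the omission certainly loses precision.** No R² is given. Below about 5% extra R², three added terms make the SE slightly worse.
- **A reader might infer that testing history belongs in every model and that allocation must be stratified by site.** The testing question is not defined as before this visit. Clients already tested may be the ones not offered a test, so in the uptake model it may overlap with who can answer. Sequence generation is not described, and altering allocation mid-trial is more than a wording change.

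**Conclusion.** The point holds as an analysis-choice problem. Two of the four Aim 1 covariates are measured after the randomised task and can be changed by it, so the adjusted effect sizes may not be the effects that the next study needs. The size of that distortion is not derivable from the documents; the figures in step 2 are illustrative. Leaving out cancer status and site is the lesser part: it is inconsistent with the stated wish to control for indication, but its cost is random error. The precision gain is about nil at 5% extra R² and 3% to 8% of the SE at 10% to 20%, all on assumed R² and ignoring what the dropped terms explain. Given the feasibility purpose, this is a worthwhile and inexpensive correction, not a threat to the trial's validity.

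**What to change.** - In the main Aim 1 models, remove the post-task anxiety score and the effectiveness rating. Adjust for education, race, clinic site and cancer status.
- Define a variable for genetic testing received before this visit. Add it where it does not overlap with eligibility for the outcome, so not in the test-uptake model.
- Report the currently specified four-covariate model as a sensitivity analysis, labelled as conditioning on post-task measures. Keep the effectiveness item for Aim 3.
- State which form holds the effectiveness item, since section 7.0 gives two locations.

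Cost: wording in section 7.0, with cancer status and site already collected. It uses one or two degrees of freedom at most, because two single terms leave and two or three enter. Any outcome variance explained by anxiety is lost from the main model; the sensitivity analysis will show how the estimates change with both post-task terms in. Where cancer status comes only from the exit survey, it will be missing for clients who do not return it, but so will education and race, which are already in the models.
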